Difficulty listening in noise is a commonly reported complaint of persons with a history of TBI although the ability of this population to cope with and listen in background noise has not been well studied (Fausti et al., 2009; Landon et al., 2012). It is not known whether they are hypersensitive to background noise as is common in cases of PTSD, are unable to focus attention on target sounds when background noise is present (e.g., listening in the dips), are unable to suppress background noise, or whether their auditory systems cannot process and separate or stream target signals from the background noise. However, difficulty listening in background noise is not unique to

TBI. It is nearly ubiquitous in person with sensorineural hearing loss due to damage to the cochlea and subsequent deterioration of the eighth nerve and central nervous system (Summers & Leek, 1998). Background noise also is problematic for young children because of central auditory immaturity (Johnson, 2000) and elderly adults due to auditory aging and cognitive decline (Humes & Floyd, 2005). For example, older adults with normal peripheral hearing usually perform similarly to younger adults on auditory language processing tasks in quiet but are more adversely affected in noise. Even after accounting for peripheral hearing loss, older adults hear speech less well in background noise, and have difficulties in attention-demanding situations such as when speech rate is increased, when processing or response rates are high, when speakers use a non-native dialect, or when linguistic, cognitive and memorial demand are increased (Burda, Scherz, Hageman & Edwards, 2003; Gordon-Salant & Fitzgibbons, 2004; Humes & Floyd, 2005; Schneider, Daneman, Murphy & Kwong, 2000). Older adults also have difficulty performing cognitive tasks (e.g., working memory tasks) in noise (Heinrich & Schneider, 2010). Older adults appear to have more difficulties with voice segregation than do young adults, which have been attributed to problems with synchrony of coding (Schneider, Daneman & Pichora-Fuller, 2002). Synchrony of coding allows access to the fine structure of speech signals, such as vocal F_0 and harmonics, and facilitates the separation of speech from background noise and co-occurring speech signals (Summers & Leek, 1998).

Although not well studied, the auditory complaints of mTBI patients with normal audiometric test results appear to be similar in nature to those ascribed to older adults with normal hearing thresholds. The parallels are of interest in accounting for and differentiating between the influences of peripheral and central auditory damage, as well as understanding mechanisms that impede efficient processing, but such an approach should be considered with caution as auditory decline in the aging model might not match with deficits associated with brain deficits due to traumatic insult.

A common model of auditory perception, the Auditory Image Model (AIM; Patterson, 2000) provides a general perspective on the possible auditory problems of blast-exposed veterans. The model argues that the auditory system forms images that are coded early at the level of the cochlea and eighth nerve, and then are integrated and processed as the auditory signals proceed through the central nervous system. Recent work looking at the response to vowels and consonant-vowel syllables at the level of the eighth nerve and subcortical regions is consistent with this notion of early coding (e.g., Aikin & Picton, 2008; Krizman, Skoe & Kraus, 2010). As such, breakdown and sensitivity to noise can occur very early in the system, and also becomes evident at higher cortical levels and possibly impacts cognitive and linguistic functions. Conversely, cognition and linguistic status can influence the manner in which primary signals and noise are processed by the auditory system. Such an approach also supports the argument that auditory perceptual learning through exposure to modified input (e.g., cochlear implants, frequency and intensity shifted feedback, spectrally shifted vowels) and targeted perceptual training can influence performance across various levels of the auditory system. However, the plasticity of the auditory system in blast-exposed patients likely is dependent on the nature and extent of their impairments.

Treatment Options

There is a range of treatments for veterans with mTBI depending on the magnitude and type of injury, the presence of comorbid injuries, time post-injury and the presenting impairments. After a patient is physically stable a number of rehabilitation approaches can be implemented (e.g., psychiatry, neuropsychology, speech-language pathology, rehabilitation and vocational counseling, physical therapy, occupational therapy), but unless a veteran has a hearing loss that is evidenced with standard audiometric test procedures the auditory intervention offerings are very limited. Blast-exposed veterans with marked auditory complaints but normal audiometric test results appear to benefit from the use of assistive listening devices such as frequency modulated (FM) systems and hearing aids with remote microphones that can be configured to reduce the impact of background noise and reverberation (See preliminary studies). There also is some evidence that these patients can benefit from auditory perceptual training procedures (Murphy et al., 2011; See preliminary studies), but acceptance and compliance with these device and behavioral treatment approaches are low.

An untested treatment option is to amplify acoustic signals with mild-gain hearing aids in order to enhance the high-frequency portion of the speech spectrum. Providing high-frequency gain can increase contrast for the high-frequency speech cues that tend to be of lower intensity and more easily masked than mid- and low-frequency cues. For example, Hornsby and Ricketts (2006) reported that by increasing high-frequency information, people with normal hearing demonstrated improved speech perception. Furthermore, even participants with flat hearing losses demonstrated substantive improvement with high-frequency emphasis. They also benefited from extended high-frequency bandwidths (Hornsby et al., 2011). Woodall and Liu (2013) similarly found that enhancing vowel second formants improved vowel discrimination in persons with high-frequency hearing loss, although the investigators did not also enhance the third formant. In addition to adding contrast, increased high-frequency gain might increase the acoustic drive to the central auditory system and reduce demands on the cognitive system. For example, Heinrich and Schneider (2011) found that older adults benefited from added gain when performing an auditory memory word-association task with distorted words, in contrast to younger adults who failed to show the benefit. They argued from a resource-allocation perspective that the added gain reduced the demands on cognitive resources that were used by the older adults to process and remember the distorted signals. [name] et al. (2007) observed a similar pattern with persons with aphasia secondary to left hemisphere stroke, where they required about +10 dB gain above that needed by non-brain-injured participants to perform an auditory language-processing task.

Another potential benefit of fitting mild-gain hearing aids on individuals with mTBI and auditory complaints is that it is a relatively passive process and more likely to be adopted than auditory training and other behavioral treatment measures because it takes less effort, and is less obtrusive and visible than personal FM systems. Furthermore, mild-gain hearing aids have the potential of stimulating auditory plasticity

and perceptual learning because they are more consistent with the natural perceptual learning process, which does not require feedback and reinforcement (Seitz & Dinse, 2007). Most perceptual learning occurs with simple exposure and without conscious effort, which is quite different from the learning processes used in most auditory training programs. So, although the use of mild-gain hearing aids will not result in substantive improvements in signal-to-noise ratio, as measured in the ear canal, the hearing aids might stimulate reorganization of the central auditory system such that there is improved filtering and segregation of signals from noise.

Although anecdotal, audiologists at the VHAPHS have been offering mild-gain open-fit hearing aids to blast-exposed veterans with normal audiometric results for the last 4 years out of frustration with the lack of practical treatment options. Patient feedback has been positive with only one patient returning his hearing aids due to tolerance problems.

3.0 Objectives

The purpose of the current proposal is to examine the characteristics and nature of this population's auditory and auditory-related skills, and assess whether coexisting PTSD contributes to their deficits. A group of these veterans will be grouped by whether they are symptomatic for PTSD, and will be compared to a control group of veterans without auditory complaints, and no PTSD or history of blast exposure. Comparisons also will be made to a group of veterans with no significant blast histories and with disabilities limited to PTSD.

After completing a clinical audiometric test battery, and PTSD, TBI, hearing handicap, and vision screens the veterans will complete measures of quality-of-life, central auditory processing, speech perception in noise, language processing and executive function to better understand various aspects of their ability to hear, remember, attend to and process speech and language through audition. The procedures will provide information about the loci of their auditory deficits and determine the extent to which language processing load and PTSD play a role. Secondarily, we will assess whether this population of veterans benefits from mild-gain open-fit hearing aids and if PTSD influences outcomes.

The information obtained from this study will help us understand the auditory problems experienced by these veterans, and eventually contribute to the development of an efficient and effective assessment battery and intervention approaches. This study is framed from both a behavioral and physiological perspective in order to document the problems experienced by this group of veterans. The tasks in the current proposal will provide insight into this population of veterans and lay the groundwork for future research looking at auditory-specific disorders secondary to blast-exposure and mTBI. The current study also will provide background support for a more extensive intervention study with this population.

Specific Questions to be Addressed

- a. Across a range of central auditory processing, speech perception, psychoacoustic, verbal working memory, and language processing tasks, does this population of veterans differ from veterans who have normal hearing and no auditory complaints? Moreover, does the coexistence of PTSD influence performance?
- b. Are certain test procedures and stimuli particularly sensitive to the deficits found with this population of veterans and are deficit patterns influenced by the coexistence of PTSD?
- c. Does the addition of background noise produce over-additive effects in this population of veterans and does PTSD increase the effect?
- d. Does this population of veterans perceive and demonstrate benefit when fitted with hearing aids that provide mild high-frequency gain and does PTSD influence benefit?
- e. Is hearing aid benefit predictable by measures of auditory processing, speech perception, psychoacoustic, verbal working memory, and language processing? Furthermore, does the coexistence of PTSD influence the relationship between these measures and hearing aid benefit?

Expected Outcomes

- a. This population of veterans will differ from veterans with no history of blast exposure, and the presence of PTSD will increase severity and alter the deficit pattern.
- b. This population of veterans will experience significant problems with the addition of background noise and the effect will be influenced by linguistic load, verbal working memory and attention.
- c. This population of veterans will demonstrate and perceive benefit from being fitted with mild-gain high-frequency hearing aids, although the coexistence of PTSD will restrict perceived benefit.
- d. Mild-gain high-frequency amplification will improve speech perception skills in quiet and noise, and improve linguistic processing and executive function.
- e. Benefit from amplification will relate to the deficits that the veterans present.

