5.0 Study Procedures

5.1 Study Design

This study will consist of two parts. Part 1 is diagnostic in nature, whereas Part 2 is a preliminary treatment study that will include a portion of the participants from Part 1.

Part 1 Procedures

The participants completing this study will be veterans between the ages of 20 and 50 years and divided into 4 groups: 2 groups of 117 veterans who report histories of blast exposure and blast-related clinical signs consistent with the VA/DoD definition of mTBI (VA/DoD, 2009) and present with normal or near normal results on standard audiometric testing but who report substantive problems with audition; a group of 117 normal hearing controls who report no auditory problems and no histories of blast exposure, brain injury, or psychiatric disorder (Normal Controls); and a group of 117 normal hearing veterans with PTSD and no blast exposure or blast-related clinical signs (PTSD-only). Of the two groups of veterans with auditory complaints one group will present with little or no PTSD (mTBI-only), whereas the other group will be symptomatic for PTSD (mTBI+PTSD). A total of 468 participants will complete the study and 50 additional participants will be allowed for experimental attrition.

In addition to the 468 veteran participants, 468 family members or friends (significant others) will complete a questionnaire about the veterans' hearing handicap.

After a telephone screen and preliminary testing, a battery of behavioral and physiological measures will be administered to all 4 groups of veterans to characterize the level and nature of their auditory impairments. Included are tests and procedures that likely will capture underlying or related problems and are commonly used in clinical and experimental studies of the peripheral auditory system, central auditory processing disorders, speech and language perception in noise, and executive function in persons with brain injury.

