- c. PTSD Checklist-Military Version (PCL-M: National Center for PTSD-Behavioral Division; Weathers et al., 1994) to screen for PTSD
- d. Hearing Handicap Inventory in Adults (HHIA, Newman et al., 1993) to document self-perceived hearing handicap. It will be administered at the beginning and end of Part 1 to document baseline handicap status prior implementing Part 2 of the study.
- e. A standard audiometric hearing test battery that includes otoscopy, tympanometry, and an acoustic reflex screen at 1000 Hz, air- and bone-conduction pure-tone threshold testing (ASHA, 2005), and the Northwestern University Test # 6 (NU-6; Tillman & Carhart, 1966)
- f. Loudness discomfort levels (LDLs) for tones at 500, 1000, 2000 and 4000 Hz according to procedures recommended by Sherlock and Formby (2005) to document hyperacusis
- g. Snellen chart to screen vision

- h. Motor-Free Visual Perception Test, version 4 (MVPT-4) to document that the subjects have the basic visual processing skills to perform tasks that include visual stimuli

Table 1. Group inclusion criteria based on preliminary test measures.

PRELIMINARY ASSESSMENT	GROUPS			
	mTBI-only	mTBI+PTSD	PTSD-only	Normal Controls
Blast Exposure History	Yes	Yes	No	No
Normal or Near Normal Standard Audiometric Test Results	Yes	Yes	Yes	Yes
History of Wearing Hearing Aids Consistently	No	No	No	No
BTI	Evidence of Brain Injury	Evidence of Brain Injury	No Evidence of Brain Injury	No Evidence of Brain Injury
PCL-M	≤ 20	> 20	> 20	≤ 20
HHIE	> 16	> 16	Not considered	≤ 16
LDLs	No Hyperacusis	No Hyperacusis	No Hyperacusis	No Hyperacusis
Snellen (corrected or uncorrected)	20/30	20/30	20/30	20/30
MVPT-4	$> 5^{\text{th}}$ percentile	$> 5^{\text{th}}$ percentile	$> 5^{\text{th}}$ percentile	$> 5^{\text{th}}$ percentile

Experiment Procedures

Part 1 Procedures

The experimental procedures are listed below according to type of assessment. Most are commonly used clinical procedures and will be completed in the standard manner.

Health and Quality of Life Questionnaires –

- a. World Health Organization Disability Assessment Schedule II (WHODAS II) as a measure of general health status and quality of life (McArdle et al., 2005)
- b. Satisfaction with Life Scale (SWLS) to document health-related quality of life
- c. Brief Symptom Inventory-18 Item (BSI-18) to document self-perceived psychiatric and psychological status

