5.6 Data Analysis

Part 1 Analysis

Preliminary Analyses - The analysis will begin with basic descriptive statistics including means and standard deviations for continuous data and examination of distributional assumptions for all study measurements including the questionnaire data (e.g., HHIA, WHODAS-II, SSQ and HHIA-SO) for each group of interest. These analyses will be used to evaluate the extent of missing data and to identify outliers.

Primary Analyses - Random Forests (RF, Breiman, 2001) will be applied to determine which auditory, language processing, and executive function variables best discriminate the three groups. This technique performs variable selection and the variables are ranked by Gini score, a measurement of average accuracy of all trees containing a particular variable. One-way ANOVA will be used to determine differences between groups for normally distributed continuous data. Analysis of covariance (ANCOVA) will be used to adjust for differences between groups. If assumptions for the parametric test are not met, a non-parametric alternative will be used (e.g., Kruskal-Wallis, non-parametric ANCOVA). The p-values will be adjusted for multiple testing by using a false discovery rate method whenever more than one variable is being tested. Statistical assumptions (e.g., linearity, normality) will be verified prior to hypothesis testing. All statistical analyses will be two sided and the significance level will be 0.05.

Sample Size and Power - A sample size of 117 per veteran group will achieve 80% power at a 0.05 significant level to detect an effect size (i.e., odds ratio) of 2.50. This sample size was computed based on an adjustment that was made assuming that a multiple regression of the independent variable of interest on the other independent

variables in the model will result in an R-squared of 0.20. For one-way ANOVA, the total sample of 468 subjects achieves 80% power to detect an effect size of 0.18 or larger with a two-sided significance of 0.01 to account for multiple hypotheses testing. For analysis of covariance, the study is powered (0.80) to detect an effect size of 0.16 assuming the strength of the relationship between the response of interest and the covariates, measured as R-squared, is 0.20.

Part 2 Analysis

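### Part 1 plans only an omnibus test across groups and names no contrast, so it cannot separate a blast/mTBI difference from a PTSD difference; the comparator in expected outcome a is also loosely worded

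*Combined protocol and SAP*

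**What the plan says.** Section 3.0 describes the comparator for the main Part 1 question in three ways.

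- Question a asks "does this population of veterans differ from veterans who have normal hearing and no auditory complaints", and then asks separately whether coexisting PTSD influences performance.
- Expected outcome a predicts "This population of veterans will differ from veterans with no history of blast exposure", and adds that PTSD will worsen severity and change the pattern of deficits.
- The opening text of the section is more exact. The blast-exposed veterans, grouped by PTSD symptoms, "will be compared to a control group of veterans without auditory complaints, and no PTSD or history of blast exposure". It continues: "Comparisons also will be made to a group of veterans with no significant blast histories and with disabilities limited to PTSD".

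Section 5.1 gives the four groups of 117: "2 groups of 117 veterans who report histories of blast exposure and blast-related clinical signs" (mTBI-only and mTBI+PTSD), PTSD-only, and Normal Controls. In Table 1 the row "Blast Exposure History" is No for both PTSD-only and Normal Controls. On hearing handicap, both mTBI groups must score above 16 and Normal Controls 16 or below; the entry for PTSD-only is "Not considered".

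Section 5.6 (Part 1, Primary Analyses) says "One-way ANOVA will be used to determine differences between groups for normally distributed continuous data". It adds ANCOVA to adjust for group differences, with no covariates named, and a non-parametric alternative such as Kruskal-Wallis. No contrast or pairwise comparison is specified. The Random Forest analysis in the same paragraph refers to three groups, although the design has four.

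**The concern.** Read literally, question a selects one comparator group (Normal Controls, 117) and expected outcome a selects two (Normal Controls and PTSD-only, 234). These give different estimates whenever PTSD affects the measure. A reader would look to section 5.6 to learn which is meant, and section 5.6 does not say. An omnibus test asks whether any of the four means differ, and a PTSD effect alone is enough to make it significant.

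At stake is the purpose of the PTSD-only group. The protocol's background calls coexisting PTSD a confounder in veterans with blast-related mTBI, and the design includes a group that allows the two to be separated. If the contrasts are left open, that separation may not be made, or the comparison may be chosen after the data are seen, across a large battery of measures.

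**Working it through.** **Inputs.** From the documents: four groups of 117 (N = 468); the significance level for tests is 0.05; the ANOVA power statement uses 0.01, 80% power and effect size f = 0.18; the ANCOVA statement gives 0.16 with covariate R-squared 0.20. Assumed, because the documents give no effect sizes by factor: SD = 1 in every group, a PTSD effect p of 0.3 SD (0.2 to 0.4 as a range), and a blast/mTBI effect b of 0 or 0.3 SD.

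**1. The plan's own figure.** One-way ANOVA with 4 groups, noncentral F, noncentrality λ = N·f². At f = 0.18 and alpha 0.01, power is 0.783; 80% power is reached at f = 0.183, which rounds to 0.18. For ANCOVA, 0.183 × √(1 − 0.20) = 0.164, which rounds to 0.16. The stated figures therefore reproduce, and they describe an omnibus test of all four groups, not a contrast.

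**2. What the omnibus test does with no blast effect.** Take b = 0, p = 0.3 and no interaction. The means are 0 (Normal Controls), 0.3 (PTSD-only), 0 (mTBI-only) and 0.3 (mTBI+PTSD). The grand mean is 0.15 and every group lies 0.15 from it, so f = 0.15 and λ = 468 × 0.15² = 10.53. With 3 and 464 degrees of freedom the rejection rate is 78% at 0.05 and 57% at 0.01. For p = 0.2 (f = 0.10, λ = 4.68) it is 41% and 20%; for p = 0.4 (f = 0.20, λ = 18.72) it is 96% and 88%.

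**3. What each possible contrast estimates.** Let I be the extra effect when both conditions are present. The means are 0, p, b and b + p + I, in the order of step 2. SE = √(Σc²/117), where c are the contrast weights. The smallest difference detectable with 80% power at two-sided 0.01 is (2.576 + 0.842) × SE = 3.417 × SE.

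| Contrast | Estimates | SE | Detectable (SD) |
|---|---|---|---|
| mTBI-only v Normal Controls | b | √(2/117) = 0.131 | 0.447 |
| mTBI+PTSD v PTSD-only | b + I | 0.131 | 0.447 |
| mTBI+PTSD v mTBI-only | p + I | 0.131 | 0.447 |
| Both mTBI v Normal Controls | b + p/2 + I/2 | √(1.5/117) = 0.113 | 0.387 |
| Both mTBI v both no-blast groups | b + I/2 | √(1/117) = 0.092 | 0.316 |
| Interaction | I | √(4/117) = 0.185 | 0.632 |

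**4. How far the comparator matters.** With b = 0.3 and I = 0, both mTBI groups against Normal Controls gives 0.30, 0.40 and 0.50 SD for p = 0, 0.2 and 0.4. Against both no-blast groups it is 0.30 SD throughout. mTBI-only against Normal Controls is also 0.30 SD throughout. With b = 0 and p = 0.4, pooling the mTBI groups against Normal Controls gives 0.20 SD and is significant at 0.01 in about 21% of trials.

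**The case against.** The strongest reply is that section 3.0 already settles the comparator. Its opening text gives a control group with no complaints, no PTSD and no blast history, and lists PTSD-only as a further comparison. Normal Controls satisfy both question a and expected outcome a. This stands. A reader might infer that the two statements set rival designs, and that the headline result depends on which one is followed. The documents do not support that, because neither statement says that the two no-blast groups are pooled.

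A reader might also infer that a PTSD effect will be reported as a blast deficit because the two mTBI groups are pooled against Normal Controls. No section plans that pooling. The groups are kept separate in sections 3.0 and 5.1, and the ANOVA power is consistent with four groups. The b + p/2 + I/2 result is only one possible reading. Question a is also descriptive: if half the population studied has PTSD, a contrast containing p/2 describes that population correctly and misleads only when read as a blast effect.

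Finally, it might be argued that the answer to question a should simply be the blast/mTBI main effect. That goes too far. The pooled no-blast comparator is not complaint-free, since PTSD-only is not selected on hearing handicap. The main effect equals b only if I = 0, whereas expected outcome a predicts that PTSD will change the deficit pattern.

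None of this supplies the missing contrasts. Section 5.6 still offers only a test that a PTSD effect alone can make significant.

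**Conclusion.** The point holds as a gap in the analysis section combined with loose wording of expected outcome a. The omnibus test planned for Part 1 does not isolate a blast/mTBI difference: with no such effect and a PTSD effect of 0.3 SD it rejects in about 78% of trials at 0.05 and 57% at 0.01. Those rates rest on an assumed PTSD effect, equal SDs, no interaction and no adjustment across measures; the false discovery rate step would change them but would not change what the test asks. The stated ANOVA and ANCOVA power figures are not in error on this point, but they do not apply to any specific comparison.

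**What to change.** In section 5.6, keep the four groups and replace the bare omnibus test with contrasts fixed in advance from a blast/mTBI by PTSD model for each Part 1 measure:

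- mTBI-only v Normal Controls, for question a with its complaint-free comparator;
- mTBI+PTSD v PTSD-only, the PTSD-matched comparison;
- the interaction, and mTBI+PTSD v mTBI-only, for the PTSD part of the question;
- the blast/mTBI main effect (both mTBI groups v both no-blast groups), reported beside the interaction as a PTSD-balanced summary, with a note that PTSD-only was not selected on hearing handicap.

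State which contrasts enter the false discovery rate adjustment. Reword expected outcome a to name the same comparators, and reconcile the reference to three groups with the four-group design.

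The cost is wording in sections 3.0 and 5.6 and a restated power paragraph, using the same data and participants. There are two downsides. Single-pair contrasts are less precise, detecting about 0.45 SD at alpha 0.01 and 80% power against about 0.32 SD for the main effect, and the interaction detects only about 0.63 SD. The blast/mTBI factor also carries the selection on auditory complaints, so no contrast in this design isolates blast exposure alone; the report should say so.
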